## 9.0 EVALUATION DURING TREATMENT/INTERVENTION

### Response assessment

Response assessment (RA) can be performed at the end of any cycle after cycle 1. Specific events that will prompt response assessment include of resolution of splenomegaly on exam and clearance of blasts from the peripheral blood, which will prompt bone marrow aspirate and biopsy. Patients continuing to maintain at least SD by the response criteria shown below should continue to receive ruxolitinib and decitabine until progression of disease, unacceptable toxicity or patient withdrawal. Patients may receive up to 24 cycles in this study. Patients may proceed to allogeneic stem cell transplant at any time after Cycle 1. Dose modification of ruxolitinib will be allowed after Cycle 1. RUXOLITINIB will be provided by the sponsor for a maximum of up to 2 years, after which it will be required to procure it from commercial sources.

Adverse events will be captured as long as patients are on study and will be used to fully characterize the tolerability and toxicity of this combination therapy. These events will be defined based on the NCI CTCAE version 4. Patients who withdraw from the study for any reason will be followed and seen 28 days (+/- 5 days) for an end of study visit to capture all adverse events.

Adverse events will only be captured after the first dose of RUXOLITINIB has been administered.

**Table 3** - Schedule of study procedures

Evaluation	Baseline screening	Cycle 1	Cycle 2 and beyond	Response assessment	End of Study
		At least once weekly (+/- 3 days)	At least once every 2 weeks (+/- 3 days)		(+/- 5 days)
History	x				
physical exam	x	x	x		x
Vital signs	x	x	x		x
Concomitant medications 	x	x	x		x
Adverse event assessment		x	x		x
HIV, HBV, HCV serology	x				
MUGA or Echo	x				
ECG	x				x
CT/MRI abd/pelvis without contrast,	x			x 	

if clinically indicated					
Pregnancy test	X				
CBC with differential	X	X	X		X
Chemistry 	X	X	X		X
Bone marrow biopsy	X			X 	X
Bone marrow aspirate	X			X 	X
Jak2/MPL allele burden 	X				
Correlative studies 	X				X
Chest X-ray	X				

1. Preferentially performed on the marrow, but will be performed on the peripheral blood if a specimen cannot be obtained. Allele burden will not be repeated if neither Jak2 nor MPL is mutated. The sample will be obtained in 5 ml EDTA tube.
2. After one cycle of therapy, after 3 cycles, and then every 3 cycles while on the study (in addition to base-line and end of the study samples), peripheral blood will be collected for measurements of inflammatory cytokine levels, expression of different proteins related to intracellular signaling, and methylation of genes. This will include collection of: one red top (10ml) and two purple top tubes (10ml each). All samples will be submitted to the laboratory of [name] at MD Anderson.
3. There are 2 milestone events that will prompt response evaluation. Resolution of palpable splenomegaly will prompt imaging of the abdomen and pelvis. Clearance of blasts from the peripheral blood will prompt bone marrow aspirate and biopsy.
4. Direct Bilirubin, Phosphorus, Albumin, PT/PTT, Alk Phos, Total Bilirubin, Total Protein, Glucose, Calcium, Magnesium, Na, K, Cl, HCO3, BUN, creatinine, AST, ALT, LDH and uric acid
5. Comcomitant medications will not be captured in CRF. Available in Clinic Station.

Testing in outside labs are allowed and the PI or treating physician must review lab results, determine clinical significance for abnormal labs and sign/date the report.

#### **End of Study Visit (Within 6 weeks of the last dose of decitabine)**

- An interval history and physical exam including ECOG PS assessment and manual measurement (in cm) of the liver and spleen from the costal margin, if palpable. Record concomitant medications
- Record Adverse Events
- Vitals (temperature, HR, BP and RR)
- ECG
- Bone marrow aspirate and biopsy (A peripheral blood sample may be substituted in patients with more than 10% blasts in the peripheral blood)
- Laboratory Assessments
  - Hematology: CBC with differential, platelets

- Chemistry: Na, K, Cl, Mg, CO2, BUN, Cr, CPK, glucose (random), Ca, Phosphorus, AST, ALT, Alk Phos, total bilirubin, LDH, total protein, albumin, uric acid
- Peripheral blood sample for scientific correlative studies: one red top tube (10ml) and two purple top tubes (10ml each).

#### Outside Physician Participation During Treatment

- MDACC physician communication with the outside physician is required prior to the patient returning to the local physician. This will be documented in the patient record.
- A letter of the local physician outlining the patient's participation in a clinical trial will request local physician agreement to supervise the patient's care (Appendix D)
- Protocol required evaluation outside MDACC will be documented by telephone, fax or e-mail. Fax and/or e-mail will be dated and signed by the MDACC physician, indicating that they have reviewed it.
- Changes in drug dose and/or schedule must be discussed with and approved by the MDACC physician investigator, or their representative prior to initiation, and will be documented in the patient record.
- A copy of the informed consent, protocol abstract, treatment schema and evaluation during treatment will be provided to the local physician.
- Documentation to be provided by the local physician will include drug administration records, progress notes, reports of protocol required laboratory and diagnostic studies and documentation of any hospitalizations.
- The home physician will be requested to report to the MDACC physician investigator all life threatening events within 24 hours of documented occurrence.
- Patients will return to MDACC every two to three months for evaluation.

## 10.0 TOXICITIES/SIDE EFFECTS

Adverse Event: An adverse event is any noxious, pathologic, or unintended change in anatomical, physiologic, or metabolic functions, as indicated by physical signs, symptoms, and/or laboratory changes occurring in any phase of the clinical trial, whether associated with drug or placebo and whether or not considered drug related. All of the following are to be considered adverse events:

- An exacerbation of a pre-existing condition
- An intercurrent illness
- Any drug interaction
- Any event related to a concomitant medication
- Development of an abnormal laboratory value or a significant change from baseline in a laboratory value within the range of normal, considered by the investigator to be clinically important
- An unexpected significant worsening of the cancer under treatment. Anticipated day-to-day fluctuations in the activity of the cancer or the anticipated progression of the cancer (other than death) should not be considered an adverse event.

Serious Adverse Event: A serious adverse event is one that is fatal or life-threatening (see below), is temporarily or permanently disabling, requires inpatient hospitalization (initial or

prolonged), or is associated with a congenital anomaly, a new cancer or a drug overdose (either accidental or intentional). In addition, any event suggesting a significant hazard, contraindication, side effect or precaution should also be considered serious. The MDACC criteria for adverse events in Leukemia will be used for reporting (Appendix E).

Life-threatening: means an immediate risk of death from the reaction as it occurred. Life-threatening does not include a reaction that, had it occurred in a more serious form, might have caused death. For example, drug-induced hepatitis that resolved without evidence of hepatic failure would not be considered life-threatening even though drug-induced hepatitis can be fatal.

The following potential adverse reactions may occur: bone marrow suppression with risks of neutropenia, anemia, and thrombocytopenia. It is anticipated that there will be a risk of infection both from myelosuppression and immunosuppression. There is a risk for developing a secondary neoplasm such as acute leukemia or myelodysplastic syndrome (MDS). Specific side effects of the drugs given during treatment are listed below:

The main anticipated side effect of treatment with Decitabine is myelosuppression. This is both expected and acceptable in this clinical setting and will be managed with standard of care practice including appropriate anti-microbial prophylaxis for bacterial, fungal and viral infections. Red blood cell transfusions are acceptable for a hemoglobin  $<8\text{g/dL}$  or higher if the investigator believes the transfusion will ameliorate symptoms of anemia. Platelet transfusions are acceptable in cases of acute bleeding or routinely for a platelet count below  $20 \times 10^9/\text{L}$ .

Treatment with Ruxolitinib would also expect to induce myelosuppression and the same standard practices listed above would apply. The clinical adverse event profile of Ruxolitinib as has been described in the published phase I/II would indicate minimal gastrointestinal and other non-hematological toxicity.

## **11.0 CRITERIA FOR THERAPEUTIC RESPONSE/OUTCOME ASSESSMENT**

Response assessment will follow the standard response assessment for AML defined by Cheson et al :

### **Complete Response (CR)**

- The subject must be free of all symptoms related to leukemia and have an absolute neutrophil count  $\geq 1 \times 10^9/\text{L}$ , no need for red blood cell transfusion, platelet count  $\geq 100 \times 10^9/\text{L}$ , and normal marrow differential ( $\leq 5\%$  blasts) in a normo- or hypercellular marrow

### **CRi**

- As per CR but incomplete count recovery.

### Partial Response (PR)

- CR with 6 – 25 % abnormal cells in the marrow or 50 % decrease in bone marrow blasts.

In addition, we will also use the response criteria recently published by Mascarenhas, et al :

**Table 4** - Response criteria for myeloproliferative neoplasm in blast phase (MPN-BP)

### Complete Molecular Response (CMR)

Description	Complete remission of both leukemia and MPN
Hematologic profile	ANC>1000 Hemoglobin>10g/dL Platelets >100 X10  /L Absence of leukoerythroblastosis 
Spleen	Non-palpable
Bone Marrow	Celullarity appropriate for age Loss of abnormal morphology Blasts ≤5%  ≤ grade 1 marrow fibrosis
Cytogenetics	Normal karyotype 
Molecular markers	Loss of any previously documented markers associated with either the leukemic or MPN clone

### Complete Cytogenetic Response (CCR)

Description	Complete remission of both leukemia and MPN
Hematologic profile	ANC>1000 Hemoglobin>10g/dL Platelets >100 X10  /L Absence of leukoerythroblastosis 
Spleen	Non-palpable
Bone Marrow	Celullarity appropriate for age Loss of abnormal morphology Blasts ≤5%  ≤ grade 1 marrow fibrosis
Cytogenetics	Normal karyotype 

Molecular markers	Residual expression of MPN mutation (e.g. Jak2V617F)
-------------------	--

#### Acute Leukemia Response- Complete (ALR-C)

Description	Complete remission of leukemia with residual MPN features
Hematologic profile	Absence of blasts 
Spleen	<25% increase in spleen size by palpation or imaging if baseline spleen <10cm or <50% if baseline spleen ≥ 10cm
Bone Marrow	Blasts ≤5% 
Cytogenetics	Loss of cytogenetic abnormality associated with leukemic clone, may have persistent abnormality associated with MPN
Molecular markers	Loss of previously identified markers in leukemic clone, may have persistent molecular markers associated with MPN

#### Acute Leukemia Response-Partial (ALR-P)

Description	Decrease in leukemic burden but without resolution of peripheral blood or bone marrow blasts and residual MPN features
Hematologic profile	>50% reduction in blasts
Spleen	<25% increase in spleen size by palpation or imaging if baseline spleen <10cm or <50% if baseline spleen ≥ 10cm
Bone Marrow	>50% reduction in blasts
Cytogenetics	No new abnormalities

Molecular markers	No new abnormalities
-------------------	----------------------

### Stable Disease (SD)

Description	Failure to achieve at least ALR-P, but no evidence of progression for at least 8 weeks.
-------------	---

### Progressive Disease (PD)

Description	Progression of leukemia and/or background MPN
Hematologic profile	For patients with 10-20% blasts: ≥50% increase to >20% blasts  For patients with >20% blasts: ≥50% increase to > 30% blasts
Spleen	>25% increase in spleen size by palpation or imaging if baseline spleen <10cm and >50% if baseline spleen ≥ 10cm
Bone Marrow	For patients with 5-10% blasts: ≥50% increase to >10% blasts  For patients with 10-20% blasts: ≥50% increase to >20% blasts  For patients with >20% blasts: ≥50% increase to > 30% blasts

## 12.0 CRITERIA FOR REMOVAL FROM STUDY

Patients may voluntarily withdraw from the study or be removed at the discretion of the investigator at any time. If such withdrawal occurs, or if the patient fails to return for visits, the investigator must determine the primary reason for a patient's premature withdrawal from the study and record this information on the appropriate eCRF. Patients may be withdrawn from the study prematurely for one of the following reasons:

- Adverse event(s)
- Abnormal laboratory value(s)
- Abnormal test procedure result(s)
- Protocol deviation
- Subject withdrew consent
- Lost to follow-up
- Administrative problems

- Death
- Initiation of new cancer therapy
- Disease progression
- The investigator determines that further therapy is not in the patient's best interest (e.g., due to non-compliance, toxicity etc.).

Patients who experience disease progression, start of new anti-cancer therapy, or withdraw consent, must be permanently discontinued from the study.

For patients who are lost to follow-up, the investigator should show "due diligence" by documenting in the source documents steps taken to contact the patient, e.g., dates of telephone calls, registered letters, etc.

## 13.0 STATISTICAL DESIGN

### **Basis for sample size:**

#### **Phase I**

First, a phase I study is performed to assess the safety of different dosing regimens for RUXOLITINIB combined with decitabine. Four combination dose levels are defined (table 1). A 3+3 design will be used to for dose escalation. Detailed dose escalation rules are described in the following section. A maximum of 18 evaluable patients will enroll in the phase I study.

#### **Dose Escalation Procedures:**

The dose of treatment agent will be escalated in successive cohorts of patients. The starting dose is at dose 0 as shown in table 1. Enroll 3 patients at the dose level and proceed to the next higher dose level with a cohort of 3 patients until at least 1 patient experiences a dose-limiting toxicity (DLT). If only 1 of 3 patients experiences a DLT at a given dose level, enter 3 additional patients at the current dose level. If only 1 of 6 patients experiences a DLT at a given dose level, proceed to the next higher dose level with a cohort of 3 patients. If at least 2 of 3 or 2 of up to 6 patients experience a DLT at a given dose level, then the MTD has been exceeded (stopping dose). Once the MTD has been exceeded, treat another 3 patients at the MTD if there were only 3 patients treated at that dose level. The MTD is defined as the highest dose level in which 6 patients were treated with at most 1 experiencing a DLT during the 1st cycle. One cycle of therapy is defined 5 days of decitabine and 28 days of RUXOLITINIB but treatment with RUXOLITINIB can be continued until the next cycle (start of decitabine) in the absence of toxicity, beyond the day 28 and without interruption.

**Table 5 - Dose levels of decitabine and RUXOLITINIB**

Dose level	Decitabine (mg/m  /d x 5 days)	RUXOLITINIB (mg PO) (x 28 days)
0 (starting dose)	20	10 BID
1	20	15 BID
2	20	25 BID
3	20	50 BID

## Phase II

Phase II part is a single arm study using the dosage level recommended from phase I. The patients treated at the MTD in phase I will not be included in phase II part, and the sample size for phase II is a maximum of 24 patients. The trial will be continuously monitored for efficacy and toxicity (non-hematological  $\geq$ grade 3 and hematological  $\geq$ grade 4). The method of Thall, Simon, and Estey will be used to perform interim efficacy and safety monitoring.

### **Efficacy and Toxicity Monitoring**

The primary endpoint is the overall response (CR+CRi) after three cycles of treatment. Overall response (OR) and toxicity will be monitored simultaneously using the Bayesian approach of Thall, Simon, Estey (1995, 1996) and the extension by Thall and Sung (1998. The historical data suggested the overall response rate is 10% and the target overall response rate with the experimental treatment is 30%. This regimen of the combination treatment will be considered worthy of further investigation if it elicits an increase in OR to 20% with acceptable toxicity. A  $>20\%$  toxicity rate is considered unacceptable. Thus, interim monitoring rules, assuming the prior distributions above, were constructed that meet the following two conditions,

$$\Pr(0.2 < \theta_{E, \text{Toxicity}} | \text{data}) > 0.80 \text{ and}$$

$$\Pr(\theta_{E, \text{OR}} > 0.3 | \text{data}) < 0.025.$$

where  $\theta_{E, \text{Toxicity}}$  and  $\theta_{E, \text{OR}}$  are the true toxicity and overall response for the combination treatment, respectively. The first rule provides for stopping the study if excessive toxicity is highly probable (i.e., probability  $>80.0\%$ ) for the combination treatment. The second condition will stop the study early if the data suggest that it is unlikely (i.e., probability  $< 2.5\%$ ) that OR rate of the combination treatment is 30%. Monitoring for toxicity and futility will not begin until 4 patients have been evaluated, and cohort size for future evaluations is 2.

The monitoring rule for the toxicity rate, based on these assumptions and monitoring conditions above is found in Table 7. For example, accrual will cease if 3 or more patients experience toxicities among the first 6 patients.

Table 7. Stop accrual if the number of toxicities is greater than or equal to indicated (i.e., # patients with toxicities) among the number of patients evaluated							
# patients evaluated	2-4	6-8	10-12	14-16	18-20	22	24
# patients with toxicities	2-4	3-8	4-12	5-16	6-20	7-22	Always stop with this many patients

Monitoring the OR rate, based on the above assumptions and monitoring conditions is found in Table 8. For example, accrual will cease if 0 or fewer patients experience a response in the first 8 patients treated.

Table 8. Stop accrual if the number with OR is less than or equal to indicated (i.e., # patients with OR) among the number of patients evaluated					
# patients evaluated	2-6	8-12	14-18	20-22	24
# patients with OR	Never stop with this many patients	0	0-1	0-2	Always stop with this many patients

Multc Lean Desktop (version 2.1.0) was used to generate the toxicity and futility stopping boundaries and the OC table (Table 9). In order to utilize the software for the design, a 30% response rate and beta (0.6, 1.4) priors were assumed for the standard treatment response distribution and experimental treatment response prior distribution, respectively. In addition, a 30% toxicity constant rate and beta (0.6, 1.4) priors were assumed for the standard treatment toxicity constant rate and experimental treatment toxicity prior distribution, respectively.

The probability of stopping the study early if the true response rate of the combination treatment was not better than 30% and the true toxicity rate is 20% was 44%. Probabilities of stopping early for high true toxicity rates (i.e., 40%) were 10% when the true OR rate was 10% and 39% when true OR rate was 20%.

Table 9. Operating characteristics for simultaneous monitoring response and toxicity rates for patients treated with combination treatment

True OR	True Toxicity Rate	True Probability Vector (OR/Tox, OR/NoTox, NoOR/Tox, NoOR/NoTox)	Probability of Stopping	Average number of patients treated
10%	10%	(0.01, 0.09, 0.09, 0.81)	0.7689	14
10%	20%	(0.02, 0.08, 0.18, 0.72)	0.8437	12
10%	30%	(0.03, 0.07, 0.27, 0.63)	0.9325	9
10%	40%	(0.04, 0.06, 0.36, 0.54)	0.9827	7
20%	10%	(0.02, 0.18, 0.08, 0.72)	0.3679	19
20%	20%	(0.04, 0.16, 0.16, 0.64)	0.5724	15
20%	30%	(0.06, 0.14, 0.24, 0.56)	0.8153	11
20%	40%	(0.08, 0.12, 0.32, 0.48)	0.9526	7
30%	10%	(0.03, 0.27, 0.07, 0.63)	0.1676	21
30%	20%	(0.06, 0.24, 0.14, 0.56)	0.4369	17
30%	30%	(0.09, 0.21, 0.21, 0.49)	0.7568	12
30%	40%	(0.12, 0.18, 0.28, 0.42)	0.9379	8
40%	10%	(0.04, 0.36, 0.06, 0.54)	0.1036	22
40%	20%	(0.08, 0.32, 0.12, 0.48)	0.3936	18
40%	30%	(0.12, 0.28, 0.18, 0.42)	0.7381	12
40%	40%	(0.16, 0.24, 0.24, 0.36)	0.9328	8

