### Analysis method

Data analysis will be performed using SAS or S-plus, as appropriate. All patients who received at least 1 dose of the combined agents will be included in the intent-to-treat analysis for efficacy. Demographic and disease characteristics of the patients at registration will be summarized using descriptive statistics such as mean, standard deviation (SD), median and range. Overall response rates will be presented with 95% confidence intervals.

The association between response and patient and disease characteristics will be examined by two-sample t-test (or Wilcoxon rank-sum test) or Chi-square test.

The data from all patients who received the combined therapy during the study will be included for safety analysis. Safety data will include laboratory, physical exam, and adverse event reports on study patients. These descriptive summaries will be provided for all patients for each safety parameter by cycle, grade, and relationship to treatment.

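### Section 13.0 calls the regimen worthy at an OR of 20% but builds its futility rule on 30%, and it misdescribes the 30% and the 44% stopping probability

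*Combined protocol and SAP*

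**What the plan says.** Under Efficacy and Toxicity Monitoring (Section 13.0), three response rates appear close together.

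- Reference: "The historical data suggested the overall response rate is 10" per cent.
- Target: "the target overall response rate with the experimental treatment is 30" per cent.
- Worthiness: the regimen is "considered worthy of further investigation if it elicits an increase in OR to 20% with acceptable toxicity".

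The futility rule is then presented as following from these statements: stop if Pr(OR > 0.3 | data) < 0.025. The explanation says the trial stops when it is unlikely "that OR rate of the combination treatment is 30" per cent. The worked example for Table 8 is that "accrual will cease if 0 or fewer patients experience a response in the first 8 patients treated".

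After Table 8, the software inputs are described: "a 30% response rate and beta (0.6, 1.4) priors were assumed for the standard treatment response distribution" and for the experimental prior. The paragraph before Table 9 gives the probability of stopping early "if the true response rate of the combination treatment was not better than 30% and the true toxicity rate is 20% was 44" per cent.

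At 24 patients Table 8 contains no count; it says only that the trial stops there. Analysis method adds: "Overall response rates will be presented with 95% confidence intervals". Section 1.2 frames the phase II primary objective as a comparison with the historical response rate on decitabine alone.

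**The concern.** The worthiness sentence is the plan's only statement of what would count as a positive phase II result, and its 20% is neither the reference (10%) nor the rate in the rule said to follow from it (30%). A reader cannot tell whether a true OR of 20% is a success or a rate the trial is meant to screen out, nor whether 20% refers to the observed proportion at the end. In a single-arm trial judged against a historical rate, results such as 5/24 or 6/24 could then be argued either way once the data are known.

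The two descriptions add to this. Calling 30% the standard-treatment rate conflicts with the historical 10%. The sentence about 44% reads as protection against an inadequate regimen, although the figure belongs to a regimen that meets its target.

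**Working it through.** **Inputs (all Section 13.0).** Prior Beta(0.6, 1.4) for both response and toxicity; futility cut-off 0.025 at threshold 0.3; toxicity cut-off 0.80 at threshold 0.2; looks at 4, 6, ..., 22; maximum 24.

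**Step 1: which threshold produced Table 8?** With x responders in n, the posterior is Beta(0.6 + x, 1.4 + n − x).

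- At 0.30, the boundary is 0 at 8–12, 1 at 14–18 and 2 at 20–22. This is Table 8 exactly.
- At 0.20, it is 0 at 12–20 and 1 at 22, which is not Table 8.
- For the worked example, 0/8, the posterior is Beta(0.6, 9.4). Pr(OR > 0.3) = 0.014, below 0.025, so stop. Pr(OR > 0.2) = 0.056, so do not stop.

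The rule was therefore run at 30%. Table 7 also reproduces exactly, at toxicity threshold 0.2.

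**Step 2: reproduce Table 9.** I used an exact recursion over (responses, toxicities), adding two independent binomial counts between looks and removing probability that crosses either boundary. Independence is what Table 9's vectors imply (for example 0.30 × 0.20 = 0.06). Of the 16 stopping probabilities, 15 agree to four decimals; the other is 0.9376 against a printed 0.9379.

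**Step 3: stopping at a true OR of 20%, both rules running.**

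| Toxicity | Futility only | Toxicity only | Both | Total (Table 9) |
|---|---|---|---|---|
| 10% | 0.2873 | 0.0779 | 0.0026 | 0.3679 |
| 20% | 0.2168 | 0.3424 | 0.0132 | 0.5724 |

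(The 10% row sums to 0.3678 from rounded parts.) Futility is met in 0.2873 + 0.0026 = 29.0% and 0.2168 + 0.0132 = 23.0%. With a 0.20 threshold these would be 8.4% and 6.4%.

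**Step 4: the 44%.** At OR 30% and toxicity 20%: 0.0650 futility only + 0.3676 toxicity only + 0.0043 both = 0.4369. Futility is met in 6.9 of the 43.7 points. At the same toxicity, Table 9 prints 0.5724 for OR 20% and 0.8437 for OR 10%.

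**Step 5: 20% as an observed rate.** The highest observed rate at any Table 8 stop is 2/20 = 10%, so no futility stop removes a trial showing 20%. At the end, 4/24 = 16.7% and 5/24 = 20.8%, so the implied count is 5. Its exact 95% interval is 7.1% to 42.2%, which includes 10%.

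**Step 6: candidate final counts.** Probability of completing 24 patients with at least this many responders under the printed Tables 7 and 8, at toxicity 10% / 20%:

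| Count | Why it is a reference point | OR 10% | OR 20% | OR 30% |
|---|---|---|---|---|
| 5/24 | smallest at or above an observed 20% | 6.9% / 4.6% | 45.3% / 30.6% | 77.8% / 52.6% |
| 7/24 | smallest whose exact 95% interval (12.6% to 51.1%) excludes 10% | 0.66% / 0.45% | 16.9% / 11.4% | 55.0% / 37.2% |
| 8/24 | smallest at or above an observed 30% | 0.15% / 0.10% | 8.1% / 5.5% | 39.5% / 26.7% |

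The 7/24 entry depends on the interval method, which Analysis method does not name. The exact interval for 6/24 (9.8% to 46.7%) includes 10%; a Wilson interval for 6/24 has a lower limit of 12.0% and does not.

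**The case against.** The strongest defence is that one word is wrong. From 10% to 30% is an increase of 20 percentage points, so *to* may be a slip for *by*. The target, the rule, its explanation and Table 8 all agree on 30%, and nothing operational would change. This is plausible, but the printed sentence is the only worthiness statement and still needs correcting.

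A reader might go further and infer that the criterion cannot be applied at all, or that the plan has no criterion at 24 patients. The documents do not support that: read as an observed rate, 20% gives 5/24 and contradicts no futility stop. What is missing is any statement that this reading is intended, and any operating characteristics for it.

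On the labels, the 30% is introduced as something needed to run the software, so it may be an input and not a claim about past response. Likewise, 44% is the lowest Table 9 stopping probability among ORs of 10%, 20% and 30% at 20% toxicity, so the sentence is not false as a minimum, and no trial decision depends on it. Both points reduce the weight of the labelling faults. They do not make the descriptions accurate.

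Finally, a monitored single-arm phase II may legitimately end in an estimate with an interval. That is fair in general, but this plan itself announces a worthiness decision, so the threshold for it should be clear.

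**Conclusion.** The inconsistency is real and should be fixed; it does not invalidate the design. The stated decision threshold (20%) is not the one in the futility rule (30%), and the plan does not say whether it is true or observed. The consequence depends on the reading: a 29.0% or 23.0% chance of meeting the futility boundary for a regimen truly at 20% (toxicity 10% or 20%), or an implied 5/24 that does not exclude the historical 10% by an exact interval. The 44% is correctly rounded but wrongly described: it is the chance of stopping at the target OR, mainly for toxicity.

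It would be wrong to infer that the boundaries or Table 9's stopping probabilities are miscalculated; they reproduce, apart from a difference of 0.0003 in one row. Nor do the documents show that the futility rule wrongly discards worthy regimens, since that holds only if 20% is a true rate worth pursuing, which they do not say.

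These results rest on the printed prior and cut-offs, looks at 4 to 22 by twos, and independence of response and toxicity as in Table 9.

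**What to change.** 1. **Reconcile the 20% with the rule.** The simplest correction is an increase of 20 percentage points, to 30%; Tables 7 to 9 stand. If an observed 20% is meant, say so. Only if a true 20% is intended, re-run Tables 8 and 9 at 0.20 and disclose the price: at OR 10%, total stopping falls from 0.769 to 0.463 (10% toxicity) or from 0.844 to 0.636 (20% toxicity), and mean patients treated rises from 13.9 to 19.2 or from 11.8 to 15.6.
2. **Correct the descriptions.** Describe 30% as the target, used as the fixed comparison in the software, with 10% as the historical reference. Describe the 44% as the chance of stopping at the target OR with 20% toxicity, mostly from the toxicity rule.
3. **State the criterion at 24 patients** as a responder count consistent with item 1, chosen by the sponsor, with its operating characteristics under both stopping rules and the interval method named. The three counts tabulated above are reference points, not recommendations. A strict count is hard to reach at this size: at OR 30%, 7/24 is reached with probability 61% even with no stopping.

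If 30% is confirmed, the cost is revised wording and a short statement of the final criterion with its operating characteristics, with no table re-run.

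### The text gives a 10% and 39% chance of stopping at 40% toxicity where Table 9 gives 98% and 95%, and it names a 30% toxicity constant where Table 7 was built on 20%

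*Combined protocol and SAP*

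**What the plan says.** All of this is in section 13.0, under Efficacy and Toxicity Monitoring.

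- **The rule.** A toxicity rate above 20% is called unacceptable. Accrual stops if the posterior probability that toxicity exceeds 0.20 is above 0.80, or if the posterior probability that OR exceeds 0.30 is below 0.025. Looks start at 4 patients and follow every 2, to a maximum of 24. Tables 7 and 8 print the boundaries, and the text illustrates Table 7 by saying "accrual will cease if 3 or more patients experience toxicities among the first 6 patients".
- **The software inputs.** For response: "a 30% response rate and beta (0.6, 1.4) priors were assumed for the standard treatment response distribution". For toxicity: "a 30% toxicity constant rate and beta (0.6, 1.4) priors were assumed for the standard treatment toxicity constant rate".
- **The performance summary.** "Probabilities of stopping early for high true toxicity rates (i.e., 40%) were 10% when the true OR rate was 10" per cent, and 39% when it was 20%.
- **Table 9.** The row for OR 10% and toxicity 40%, with probability vector "0.04, 0.06, 0.36, 0.54", has a stopping probability of 0.9827. The row for OR 20% and toxicity 40% has 0.9526. The row for OR 40% and toxicity 10%, with vector "0.04, 0.36, 0.06, 0.54", has 0.1036, and the row for OR 40% and toxicity 20% has 0.3936.

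**The concern.** The summary sentence and the table below it give opposite accounts of the same scenarios. Read alone, the sentence says that a regimen toxic in four patients out of ten would usually run to full accrual. It is the only sentence in the plan that says how the design behaves when toxicity is high, so an ethics committee or monitor relying on it would misjudge the protection patients have.

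The stated 30% constant raises a separate problem. It tells the reader how to regenerate the boundaries, yet it differs from the 0.20 in the rule. Someone who re-ran the monitoring with 30%, for instance after a change in sample size or look schedule, would get a more permissive safety rule than Table 7 without any warning.

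**Working it through.** **Inputs.** Prior Beta(0.6, 1.4), cut-offs 0.80 (toxicity) and 0.025 (response), looks at n = 4, 6, ..., 22, maximum 24. Reaching 24 is not counted as early stopping. Response and toxicity are independent, as Table 9's vectors imply (for example 0.10 × 0.40 = 0.04 in the first cell of the OR 10%, toxicity 40% row).

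**Step 1: boundaries.** After x toxicities in n patients the posterior is Beta(0.6 + x, 1.4 + n − x). The boundary is the smallest x for which Pr(toxicity > c | data) exceeds 0.80.

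| n | Table 7 | c = 0.20 | c = 0.30 |
|---|---|---|---|
| 4 | 2 | 2 | 3 |
| 6 | 3 | 3 | 3 |
| 8 | 3 | 3 | 4 |
| 10 | 4 | 4 | 5 |
| 12 | 4 | 4 | 6 |
| 14 | 5 | 5 | 6 |
| 16 | 5 | 5 | 7 |
| 18 | 6 | 6 | 8 |
| 20 | 6 | 6 | 8 |
| 22 | 7 | 7 | 9 |

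For example, 2 toxicities in 4 patients give a posterior probability of 0.886 with c = 0.20 (stop) but 0.734 with c = 0.30 (continue). The value 0.20 reproduces every entry of Table 7; 0.30 agrees only at n = 6. For response, the 0.30 threshold with the same prior reproduces every entry of Table 8.

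**Step 2: each rule alone.** Exact enumeration over the looks gives these probabilities of stopping early:

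- Toxicity rule, Table 7 boundaries: 0.0832, 0.3798, 0.7321 and 0.9313 at true toxicity of 10%, 20%, 30% and 40%.
- Futility rule, Table 8 boundaries: 0.7479, 0.3105, 0.0920 and 0.0222 at true OR of 10%, 20%, 30% and 40%.

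**Step 3: both rules together.** Under independence, P(stop) = 1 − (1 − P_tox)(1 − P_fut).

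| True OR | True toxicity | Calculation | Result | Table 9 | Text |
|---|---|---|---|---|---|
| 30% | 20% | 1 − 0.6202 × 0.9080 | 0.4369 | 0.4369 | 44% |
| 10% | 40% | 1 − 0.0687 × 0.2521 | 0.9827 | 0.9827 | 10% |
| 20% | 40% | 1 − 0.0687 × 0.6895 | 0.9526 | 0.9526 | 39% |
| 40% | 10% | 1 − 0.9168 × 0.9778 | 0.1036 | 0.1036 | – |
| 40% | 20% | 1 − 0.6202 × 0.9778 | 0.3936 | 0.3936 | – |

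Fifteen of the 16 rows of Table 9 match to four decimals. The other (OR 30%, toxicity 40%) computes to 0.9376 against 0.9379 printed, which is immaterial.

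The text's 10% and 39% cannot be right for 40% toxicity at any response rate, because the toxicity rule alone already stops with probability 0.9313. The errors are 98.3 − 10 ≈ 88 and 95.3 − 39 ≈ 56 percentage points.

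**Step 4: what a 30% constant would do.** With the c = 0.30 boundaries the toxicity rule alone stops with probability 0.1349, 0.4081 and 0.7296 at toxicity of 20%, 30% and 40%. Combined with futility:

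| True OR | True toxicity | With c = 0.30 | Table 9 |
|---|---|---|---|
| 30% | 20% | 1 − 0.8651 × 0.9080 = 0.2145 | 0.4369 |
| 30% | 30% | 1 − 0.5919 × 0.9080 = 0.4626 | 0.7568 |
| 30% | 40% | 1 − 0.2704 × 0.9080 = 0.7545 | 0.9379 |
| 10% | 40% | 1 − 0.2704 × 0.2521 = 0.9318 | 0.9827 |
| 20% | 40% | 1 − 0.2704 × 0.6895 = 0.8136 | 0.9526 |

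So 30% generates neither Table 7 nor Table 9, and it does not rescue the text's 10% and 39% either. At OR 30% and toxicity 40%, average enrolment would rise from about 8 patients to about 12.

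**The case against.** The strongest reply is that conduct is safe. Accrual is governed by Tables 7 and 8 and by the displayed 0.20 condition. These agree with one another, with the statement that toxicity above 20% is unacceptable, and with Table 9, which sits directly below the faulty sentence. A team applying the printed tables would stop when it should. That stands, and it limits the harm to readers who rely on the prose or rebuild the design from it. It does not make the prose right.

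Four narrower points also stand:

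- The sentence is not the only prose on stopping. The one before it correctly gives 44% at OR 30% and toxicity 20%. It is the only one about high toxicity.
- The 98% and 95% combine two rules. At OR 10% futility alone stops with probability 0.75; the toxicity rule alone contributes 0.93 at 40% toxicity. The 88- and 56-point gaps are differences between text and table, not a measure of the safety rule by itself.
- The example of 3 toxicities among 6 patients does not separate 0.20 from 0.30, because the boundary at n = 6 is 3 under both. The evidence lies at n = 4 and from n = 8 onward.
- The software inputs are not visible. Beta(0.4, 1.6) with a 0.20 threshold gives the same Table 7 boundaries, so the table does not identify the prior. Beta(0.6, 1.4) has mean 0.6/2.0 = 0.30, so the prior may be misdescribed as well as the constant. Likewise, the exchange of labels is an inference from matching numbers, though a strong one.

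**Conclusion.** Both parts hold. The sentence on 40% toxicity understates the probability of stopping by about 88 points (10% against 98%) and 56 points (39% against 95%); Table 9 is right and the sentence is wrong. The stated 30% toxicity constant contradicts the plan's 0.20 rule and is not the threshold behind Tables 7 and 9.

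These conclusions assume independent response and toxicity (as in Table 9), looks at 4 to 22 patients, and the stated Beta(0.6, 1.4) prior. The contradiction between sentence and table needs no assumption at all. The mismatch is shown for the constant only; whether the toxicity prior is correctly described cannot be settled from the documents. Because the text misstates a safety property and a design input, it must be corrected, even though the printed boundaries are sound.

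**What to change.** Change two sentences in section 13.0.

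1. Restate the performance summary to agree with Table 9, for example: at a true toxicity rate of 40%, the trial stops early with probability 98% if the true OR rate is 10% and 95% if it is 20%. If the authors meant to show the risk of stopping a promising regimen, add that at a true OR rate of 40% the probabilities are 10% and 39% for toxicity rates of 10% and 20%.
2. Change the stated toxicity constant from 30% to 20%, to agree with the plan's own 0.20 rule and Table 7. Check the saved software inputs first, and confirm or correct the toxicity prior at the same time.

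The cost is two sentences and one look at the saved input file. No boundary, table, sample size or trial procedure changes.
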